## 5.8. Exposure to Treatment

The duration of treatment, the number of subjects who prematurely discontinued IMP, the reasons for treatment discontinuation, treatment compliance, and average daily dose of IMP will be summarized by treatment group for the FAS population.

## 5.9. Primary Efficacy Analysis

### 5.9.1. Primary Estimand

The key research question for the primary endpoint will be addressed with an estimand based on the following attributes:

1. Treatments: treatments as randomized regardless of the actual treatment received.
2. Target study population of interest: subjects in the mITT population.
3. Endpoint of interest: Change from Baseline to Week 6 in total PANSS score.
4. Population level summary of interest: the treatment differences estimated based on the least square mean and the corresponding 95% confidence interval from the mixed model of repeated measures (MMRM) model of the emraclidine groups and placebo group in the endpoint of interest.

5. Strategy for Intercurrent events (ICEs): A hypothetical strategy to address ICEs of potential death, treatment discontinuations, missed visits, and start of prohibited concomitant medications will be utilized. The data after the start of prohibited concomitant medications (ATC classifications of BUTYROPHENONE DERIVATIVES, INDOLE DERIVATIVES, and OTHER ANTIPSYCHOTICS) after the first dose of IMP and prior to the last dose of IMP with use duration of use of at least 4 days will be censored under the hypothetical strategy. The hypothetical strategy allows the study to assess the effect of emraclidine treatment without the confounding effect of prohibited concomitant treatments.

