9.3.2 Primary Endpoint/Estimand Analyses

The primary estimand has the following attributes:

1. Treatments as randomized
2. mITT population as the primary population of interest
3. Change from Baseline to Week 6 in total PANSS score as the primary endpoint of interest
4. The population level summary of interest is the treatment differences estimated based on the least square mean and the corresponding 95% confidence interval from the MMRM model with treatment, visit, and treatment by visit interaction as fixed effect, participant as a random effect, and baseline PANSS score as a covariate. An unstructured covariance structure will be used for the repeated measures. The Kenward-Roger approximation will be used to estimate the denominator degrees of freedom. If the unstructured covariance matrix results in convergence issue, the heterogeneous Toeplitz covariance structure followed by the heterogeneous first-order autoregressive (AR(1)) structure will be used. If a reduced covariance matrix becomes necessary, the sandwich variance estimator will be used.
5. To address ICEs with the primary outcome data available, a treatment policy strategy will be used to include all collected outcomes in the primary statistical analysis, consistent with the intent-to-treat principle. The only exception will be the cases of concomitant use of protocol prohibited other antipsychotic and, in such cases, the data collected under the influence of confounding ICEs will be treated as missing.
6. To address ICE of trial or treatment discontinuation with no outcome data collected post discontinuation, the primary analysis of MMRM described above will be followed by PMM approach with varying level of shift parameters for missing values due to discontinuations that are potentially missing not at random (MNAR), including discontinuation due to lack of efficacy or due to adverse events. This will be implemented using delta adjustment imputation method. Further details will be described in the SAP.

The statistical hypothesis testing on the primary endpoint (H_1 and H_2 above) will be based on the estimated treatment difference from the model at Week 6. The evaluation of other time points will also be derived from the same model.

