### **5.9.2. Main Analytical Approach**

The change from baseline to each study visit in total PANSS score will be summarized by visit and treatment group. A MMRM analysis will be used to analyze the data from all post-randomization timepoints up to Week 6 with treatment, geographic region, visit, and treatment by visit interaction as fixed effect, subject as a random effect, and baseline PANSS score as a covariate. An unstructured covariance structure will be used for the repeated measures. If the unstructured covariance matrix results in convergence issue, the heterogeneous Toeplitz covariance structure followed by the heterogeneous first-order autoregressive (AR(1)) structure will be used. The Kenward-Roger approximation will be used to estimate the denominator degrees of freedom. The difference between each emraclidine dose group and placebo at Week 6 will be estimated based on the Least Squares Mean (LSMean) difference between the treatment groups at Week 6 from the MMRM with the associated 95% confidence interval (CI) and P-value. A Cohen's D value will be derived as the ratio of the estimated difference to the population standard deviation at each visit estimated from the model (the square root of the diagonal elements of the estimated covariance matrix). The missing values are assumed to be missing at random for the main analysis, including missing due to missed visits or early termination due to COVID-19 control measures. The LSM ( $\pm$ SE) from the model will be plotted for change in PANSS total score by visit and treatment group. Similarly, the mean ( $\pm$ SD) of absolute values and change from Baseline PANSS total score will be presented by visit and treatment group.

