### Considerations of Data Potentially Missing Not at Random (MNAR)

A pattern mixture model (PMM) approach will be used to address potential MNAR patterns. The following three patterns of subjects in the mITT set will be considered:

1. Subjects with no missing values from discontinuation or from initiation of prohibited concomitant medication during treatment period (No missing)
2. Subjects with missing values from the types of ICEs below will be considered having MNAR:
  - a. Subjects who discontinue due to reasons, as recorded on the eCRF, of lack of efficacy, adverse events related to schizophrenia defined by AEHLGT of Schizophrenia and other psychotic disorders, physician decision, and withdrawal by subject
  - b. Subjects who initiated concomitant prohibited medications (ATC classifications of BUTYROPHENONE DERIVATIVES, INDOLE DERIVATIVES, and OTHER ANTIPSYCHOTICS) after the first dose of IMP and prior to the last dose of IMP with use duration of use of at least 4 days will be considered having a potential confounding ICE. The efficacy data post the start of ICE will be treated as missing with the missing pattern of MNAR.

The MNAR cases will be identified and documented prior to database lock and unblinding ([Section 9.5](#)).

3. Subjects with missing values from the type of ICEs below will be considered as having MAR
  - a. Missing values after discontinuation due to reasons, as recorded on the eCRF, of death, pregnancy, loss to follow-up, adverse event unrelated to schizophrenia, non-compliance, site termination, and COVID-19 control measures will be considered as MAR.

The missing data with MNAR pattern #2 above in the active treatment groups will be imputed tipping point analysis. A set of shift parameters to encapsulate the change in efficacy associated with MNAR due to ICEs for each of the active treatment groups will be applied in the tipping point multiple imputation analysis as described in [Ratitch et al. \(2013\)](#). It is noted, however, MNAR in the placebo group will be imputed as MAR using the standard multiple imputation method.

The MAR pattern #3 above will be imputed using the standard multiple imputation method described above.

Other missing values due to missed visits/assessments before endpoint or discontinuation will also be assumed as MAR and imputed using the standard multiple imputation method for all three patterns.

Core codes for MAR and MNAR imputations are provided in [Section 9.6](#).

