## 5.11. Summary of Primary and Key Secondary Efficacy Analyses

ICE Strategy	Primary Analysis	Sensitivity Analysis	Subgroup Analysis
Primary Endpoint: Change from Baseline to Week 6 in the PANSS total score			
Hypothetical strategy with data after treatment discontinuations or after the start of prohibited concomitant medications censored	
 
• mITT population
 
• Treatment as randomized
 
• MMRM described in Section 5.9.2
 
	
 
• Treatment effect based on actual treatment received, if applicable
 
• Missing values imputation using multiple imputations (MI)
 
• Missing values imputation using pattern mixture model (PMM)
 
• Endpoint completer analysis
 
	
 
• Age
 
• Sex
 
• Baseline PANNS Total Score
 
• Baseline CGI-S
 
• Race
 
• Region
 

Key Secondary Endpoint: Change from Baseline to Week 6 in the CGI-S score			
Hypothetical strategy with data after treatment discontinuations or after the start of prohibited concomitant medications censored	
 
• mITT population
 
• Treatment as randomized
 
• MMRM described in Section 5.9.2
 
	
 
• Treatment effect based on actual treatment received, if applicable
 
• Missing values imputation using multiple imputations (MI)
 
• Missing values imputation using pattern mixture model (PMM)
 
• Endpoint completer analysis
 
	
 
• Age
 
• Sex
 
• Baseline PANNS Total Score
 
• Baseline CGI-S
 
• Race
 
• Region
 

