## 6. CHANGES IN THE PLANNED ANALYSES

Should any deviations from the analyses specified in the authorized statistical analysis plan arise, such deviations will be documented in the final clinical study report.

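### The protocol and the SAP state different primary estimands, and the SAP's unexplained 4-day rule keeps scores taken during 1-3 days of prohibited antipsychotic use, with no visible analysis testing it

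*SAP*

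**What the plan says.** Protocol 9.3.2 says that, for intercurrent events with outcome data available, "a treatment policy strategy will be used to include all collected outcomes in the primary statistical analysis". Its sole exception is concomitant use of another, prohibited antipsychotic, where "the data collected under the influence of confounding ICEs will be treated as missing". Protocol 9.3.3 carries the same strategies over to CGI-S.

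SAP 5.9.1 applies a hypothetical strategy to death, treatment discontinuation, missed visits and the start of prohibited medication. Its data rule names three ATC classes (butyrophenone derivatives, indole derivatives, other antipsychotics) started between the first and last IMP dose. Data after such a start "with use duration of use of at least 4 days will be censored under the hypothetical strategy". The stated purpose is an effect of emraclidine "without the confounding effect of prohibited concomitant treatments". SAP 5.10.1 uses the same terms for CGI-S. In SAP 5.9.3.2, the pattern-mixture analysis uses the same filter: users of those classes "with use duration of use of at least 4 days will be considered having a potential confounding ICE".

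The model in SAP 5.9.2 takes whatever the rule leaves in: "A MMRM analysis will be used to analyze the data from all post-randomization timepoints up to Week 6". The SAP 5.11 table describes the strategy more broadly: "Hypothetical strategy with data after treatment discontinuations or after the start of prohibited concomitant medications censored". SAP 6 provides only for the case "Should any deviations from the analyses specified in the authorized statistical analysis plan arise", and the revision table in SAP 7 has no entries.

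**The concern.** The two documents differ both in the strategy they name and in the scores they admit to the H1-H4 tests. The protocol's exception is triggered by antipsychotic influence. The SAP's rule is triggered by class and length of use. A participant with one to three days of use falls under the exception and outside the SAP rule, so that participant's scores stay in, including any taken on a day of use.

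This runs against the protocol and also against the SAP's own aim of excluding the effect of prohibited treatment. If short use is more common in one arm, or acts differently across arms, the retained scores move the Week 6 difference. Because the first hypothesis gates all the others, the rule should be settled and justified before unblinding.

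**Working it through.** **Step 1. The rules side by side**

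| | Protocol 9.3.2 / 9.3.3 | SAP 5.9.1 / 5.10.1 / 5.9.3.2 | SAP 5.11 |
|---|---|---|---|
| Strategy | Treatment policy, one exception | Hypothetical | Hypothetical |
| Medication trigger | Any prohibited other antipsychotic | Three ATC classes | Prohibited medication, no class given |
| Minimum duration | None stated | 4 days | None stated |
| Scores removed | Those under the influence (period undefined) | All after the start | All after the start; also after treatment discontinuation |

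**Step 2. A worked case**

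PANSS and CGI-S are scheduled on Days 7, 14, 21, 28, 35 and 42 (Protocol 1.3), and dosing runs to Day 45. Take an antipsychotic in one of the three classes, used on Days 40-42.

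- Duration of use: 42 - 40 + 1 = 3 days, which is below 4.
- SAP 5.9.1: not censored, so the Day 42 score enters the model.
- Protocol 9.3.2: the score is taken on a day of use. Any reasonable meaning of influence covers it, so it is missing.

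The same holds for CGI-S.

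**Step 3. Does any planned analysis vary the rule?**

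- Actual treatment received (SAP 5.9.3.1): changes the arm label only.
- Multiple imputation under MAR (5.9.3.2): fills missing values and leaves kept scores alone.
- Endpoint completers (5.9.3.2): same model on fewer participants, same rule.
- Pattern mixture (5.9.3.2): repeats the 4-day, three-class filter.
- Delta shift (9.6.2): applies only to records flagged as imputed, so a kept score is never shifted.

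None does. SAP 9.5, the list of MNAR cases, and one analysis population in SAP Table 3 are not visible in the public documents, so this statement covers visible analyses only.

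**Step 4. Scale**

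The documents give no frequency of short use, no effect of it on PANSS and no SD for CGI-S. As an assumption only, suppose a kept Week 6 PANSS score differs by 5-10 points from what the model would otherwise imply. Treating the Week 6 estimate as a simple mean of 93 per arm, each net such score in one arm moves the difference by 5/93 = 0.05 to 10/93 = 0.11 point, in either direction.

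**Step 5. Cost of removing the threshold**

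The plan's own figure comes first. With 93 completers per arm, effect size 0.48 and two-sided alpha 0.05, the two-sample t-test (noncentral t) has power 0.9025; 92 per arm gives 0.8994. Then 93/(1 - 0.25) = 124 per arm, and 3 × 124 = 372. The sample size reproduces.

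At 7/14.6 = 0.479, power with 93 per arm is 0.902. Assumed extra missing scores at Week 6 give:

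- 2%: 93 × 0.98 = 91.14 per arm, power 0.896.
- 5%: 93 × 0.95 = 88.35 per arm, power 0.887.

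**The case against.** The strongest reply is that Protocol 9.3.1 leaves full analysis details to the SAP. The protocol never defines influence, and the SAP takes up the same term and sets it at four days or more, in matching words in three places. On this view the SAP only makes the protocol operational. Part of this stands: the protocol's lack of a duration limit is silence, and the SAP may fill it. But filling it does not extend to replacing treatment policy with a hypothetical strategy, and a definition that keeps a score taken on a day of use does not fit the term it defines. No reason for four days is given.

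A second reply is that few scores are at stake. Antipsychotics are prohibited and participants are inpatients. After early termination the schedule has only a follow-up contact. Protocol 7.2 and schedule footnote g rule out the efficacy scales once an antipsychotic has been started. The change of label alone may indeed affect few scores. However, those two provisions concern early discontinuation, and a participant who stays in the trial after brief use can still be rated.

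Some stronger readings are tempting but are not supported:

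- A reader might take SAP 5.11 as a third, competing data rule. It is a summary and reads as shorthand for 5.9.1. Taken literally it would censor scores after an unapproved vitamin, which Protocol Table 5 also prohibits.
- A reader might call it an error that a 4-day course on Days 2-5 removes all six scores, including Day 42, which is 42 - 5 = 37 days later. Dropping everything after the event is an ordinary way to carry out a hypothetical strategy.
- A reader might infer that a single depot injection always escapes the rule. That depends on how its dates are recorded, which the documents do not show.
- A reader might infer that some antipsychotics lie outside the three classes. The documents do not establish this.

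**Conclusion.** The point holds as a should-fix matter. The protocol and the SAP state different primary and key secondary estimands. The SAP rule keeps PANSS and CGI-S scores taken during or after 1-3 days of antipsychotic use, against the protocol's exception and the SAP's own aim. The cut-off is unjustified and the departure unrecorded. The 5.11 summary omits the class and duration limits, and no visible analysis tests the rule.

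The textual conflict needs no assumption. Its effect on the result is unknown. A reader might infer that the primary result will be biased, or biased in favour of emraclidine, but the documents support neither: frequency, size and direction cannot be derived from them. The 0.05-0.11 point per score rests on the assumed 5-10 point shift and a simple-mean approximation.

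Nor do the documents show that the protocol's rule must be the primary one. Applying it as worded needs a period of influence that neither document defines.

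**What to change.** Before unblinding:

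1. Reconcile Protocol 9.3.2 and 9.3.3 with SAP 5.9.1, 5.9.3.2, 5.10.1 and 5.11, so that one intercurrent-event strategy and one data rule apply. Record and justify any departure from the protocol in the SAP.
2. Either remove the 4-day threshold, so that PANSS and CGI-S scores after the start of any prohibited antipsychotic are missing in the primary and key secondary analyses, or keep it and state the reason.
3. If it is kept, add a sensitivity MMRM for both endpoints that sets to missing every score after the start of any prohibited antipsychotic, whatever its class or duration. If it is removed, run the 4-day, three-class rule as the sensitivity analysis.
4. Make SAP 5.11 refer to the 5.9.1 rule, and state whether scores collected after treatment discontinuation but before any antipsychotic are kept.

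The cost is wording plus one extra model run per endpoint. No new data are needed, since medication start and end dates are already collected (Protocol 6.7.1). Removing the threshold adds some missing Week 6 scores, with the small loss of power shown above.

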### **5.9.2. Main Analytical Approach**

The change from baseline to each study visit in total PANSS score will be summarized by visit and treatment group. A MMRM analysis will be used to analyze the data from all post-randomization timepoints up to Week 6 with treatment, geographic region, visit, and treatment by visit interaction as fixed effect, subject as a random effect, and baseline PANSS score as a covariate. An unstructured covariance structure will be used for the repeated measures. If the unstructured covariance matrix results in convergence issue, the heterogeneous Toeplitz covariance structure followed by the heterogeneous first-order autoregressive (AR(1)) structure will be used. The Kenward-Roger approximation will be used to estimate the denominator degrees of freedom. The difference between each emraclidine dose group and placebo at Week 6 will be estimated based on the Least Squares Mean (LSMean) difference between the treatment groups at Week 6 from the MMRM with the associated 95% confidence interval (CI) and P-value. A Cohen's D value will be derived as the ratio of the estimated difference to the population standard deviation at each visit estimated from the model (the square root of the diagonal elements of the estimated covariance matrix). The missing values are assumed to be missing at random for the main analysis, including missing due to missed visits or early termination due to COVID-19 control measures. The LSM ( $\pm$ SE) from the model will be plotted for change in PANSS total score by visit and treatment group. Similarly, the mean ( $\pm$ SD) of absolute values and change from Baseline PANSS total score will be presented by visit and treatment group.

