6. To address ICE of trial or treatment discontinuation with no outcome data collected post discontinuation, the primary analysis of MMRM described above will be followed by pattern mixture model (PMM) approach with varying level of shift parameters for missing values due to discontinuations that are potentially missing not at random (MNAR), including discontinuation due to lack of efficacy or due to adverse events. This will be implemented using delta adjustment imputation method. Further details will be described in the statistical analysis plan (SAP).

The statistical hypothesis testing on the primary endpoint (emraclidine 30 mg QD vs placebo and emraclidine 15 mg QD vs placebo) will be based on the estimated treatment difference from the model at Week 6 and will be tested in a hierarchical order with each at 2-sided alpha level 0.05. The evaluation of other time points will also be derived from the same model.

The number and proportion of responders (ie, participants with 30% reduction from Baseline in the PANSS total score at Week 6 or the last assessment before discontinuation) will be summarized. A logistic regression model, with baseline PANSS as a covariate, will be used to compare the proportion of responders in each active arm with placebo. If expected counts are <5, then a Fisher's Exact test will be used.

The secondary estimand has the following attributes:

1. Treatments as randomized
2. mITT population as the primary population of interest
3. Change from Baseline to Week 6 in CGI-S score as the endpoint of interest
4. The population level summary of interest is the treatment differences estimated based on the least square mean and the corresponding 95% confidence interval from the MMRM model with treatment, visit, and treatment by visit interaction as fixed effect, participant as a random effect, and baseline CGI-S score as a covariate. An unstructured covariance structure will be used for the repeated measures. If the unstructured covariance matrix results in convergence issue, the heterogeneous Toeplitz covariance structure followed by the heterogeneous first-order autoregressive (AR(1)) structure will be used. When a reduced covariance matrix is used, the sandwich variance estimator will be used. The Kenward-Roger approximation will be used to estimate the denominator degrees of freedom.
5. ICEs will be addressed using the same strategies as described above for the primary endpoint.

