## 1.2. Sample Size Considerations

A sample size of approximately 93 subjects in each treatment group completing the Week 6 assessments (approximately 279 in total) should provide at least 90% power to detect an effect size of 0.48 in change from Baseline in the Positive and Negative Symptom Score (PANSS) total score at Week 6 between either active treatment group versus placebo at the  $\alpha=0.05$  level. The effect size of 0.48 represents a clinically meaningful effect on symptom reduction based on large scale meta-analysis of historical data from several currently approved antipsychotic medications in common usage ([Leucht et al, 2013](#)). It could be translated into a difference of 7 points versus placebo if the standard deviation of change from baseline is 14.6 points or a difference of 8 points versus placebo if the standard deviation of change from baseline is 16.7 points. Both scenarios of the standard deviation are consistent with historical observations. To account for a discontinuation rate of approximately 25% for a 6-week treatment period (as observed in Trial CVL-231-SCH-001), it is planned to randomize approximately 372 subjects.

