## 5.5. Strata and Covariates

Randomization was stratified by geographic region with two strata: United States or Other Countries.

The baseline value of each efficacy variable will be included as a covariate in the efficacy analyses.

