### **5.10.2. Main Analytical Approach**

Similar to the analysis of the primary efficacy variable, the change from baseline to each study visit in CGI-S score will be summarized by visit and treatment group. A MMRM analysis will be used with treatment, geographic region, visit, and treatment by visit interaction as fixed effect, subject as a random effect, and baseline CGI-S score as a covariate. An unstructured covariance structure will be used for the repeated measures. If the unstructured covariance matrix results in convergence issue, the heterogeneous Toeplitz covariance structure followed by the AR(1) structure will be used. The Kenward-Roger approximation will be used to estimate the denominator degrees of freedom. The difference between each emraclidine dose group and placebo at Week 6 will be estimated based on the LSMean difference between the treatment groups at Week 6 from the MMRM with the associated 95% CI and p-value. A Cohen's D value will be derived as the ratio of the estimated difference to the population standard deviation at each visit estimated from the model (the square root of the diagonal elements of the estimated covariance matrix). The missing values are assumed to be missing at random for the main analysis, including missing due to missed visits or early termination due to COVID-19 control measures. The LSM ( $\pm$ SE) from the model will be plotted for change in CGI-S score by visit and treatment group. Similarly, the mean ( $\pm$ SD) of absolute values and change from Baseline CGI-S score will be presented by visit and treatment group.

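### The PANSS and CGI-S MMRMs use one baseline slope for six visits; a baseline-by-visit term could sharpen the Week 6 contrast at almost no cost

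*SAP*

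**What the plan says.** The primary model in SAP 5.9.2 will "analyze the data from all post-randomization timepoints up to Week 6". Its fixed effects are treatment, geographic region, visit and treatment by visit, with baseline PANSS as a single covariate: "treatment by visit interaction as fixed effect, subject as a random effect, and baseline PANSS score as a covariate". SAP 5.10.2 repeats the structure for CGI-S: "treatment by visit interaction as fixed effect, subject as a random effect, and baseline CGI-S score as a covariate". The general rule in SAP 5.5 goes no further: "The baseline value of each efficacy variable will be included as a covariate in the efficacy analyses". Protocol 9.3.2 has the same baseline term ("participant as a random effect, and baseline PANSS score as a covariate"), and 9.3.3 matches it for CGI-S. No baseline-by-visit interaction appears in any of these sections.

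On covariance, SAP 5.9.2 states: "An unstructured covariance structure will be used for the repeated measures". The Schedule of Assessments places PANSS and CGI-S at Weeks 1 to 6, which gives six post-baseline visits. The hypotheses in SAP 5.3 and 5.4 all concern Week 6, and the protocol synopsis says that the primary comparisons "will be tested in a hierarchical order with each at 2-sided alpha level 0.05".

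**The concern.** With baseline as a main effect only, the model assumes that baseline severity predicts change equally at Week 1 and Week 6. If it does not, the fitted slope is a compromise weighted by the inverse covariance of the visits. Where early visits are less variable, that compromise sits close to the early slope. Week 6, the only visit tested, then receives too little baseline adjustment, and the leftover baseline variation goes into its residual variance. The stake is the width of the Week 6 confidence interval. Cohen's D is also touched, because SAP 5.9.2 divides by the model-based SD at each visit.

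**Working it through.** **The plan's own figure.** SAP 1.2 says that 93 completers per arm "should provide at least 90% power to detect an effect size of 0.48 in change from Baseline". For 7 points and SD 14.6, the SE is 14.6 × √(2/93) = 2.141 and 7/2.141 = 3.27, so power is Φ(3.27 − 1.96) = 90.5%. Then 93/0.75 = 124 per arm, or 372 in all. The figures reproduce, and they use the SD of change with no credit for baseline adjustment.

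**Formula.** Let b be the vector of true slopes of change on baseline by visit, S the residual covariance, σ_B the baseline SD and s6 the Week 6 residual SD.
- Limit of the single fitted slope: b* = (1′S⁻¹b)/(1′S⁻¹1).
- Week 6 variance with the common slope: s6² + (b6 − b*)²σ_B². With slopes by visit it is s6².
- Proportional inflation: v = (b6 − b*)²σ_B²/s6². Equivalent completers: 279 × v/(1 + v).

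**Inputs not in the documents, all assumed.** These are the slopes, the baseline SD, the residual SDs at earlier visits and the correlation between visits. Eligibility (PANSS 85 to 120) limits baseline spread: a uniform distribution over that range has SD 35/√12 = 10.1.

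**One case in full.** Take slopes in equal steps from −0.10 (Week 1) to −0.40 (Week 6), σ_B = 9, AR(1) correlation 0.85, and residual SD rising from 8 to s6.
- s6² = 14.6² − 0.40² × 9² = 213.16 − 12.96 = 200.20, so s6 = 14.15.
- Week 1 takes a weight of 0.93 in b*, which comes to −0.125.
- v = (0.40 − 0.125)² × 81/200.20 = 3.1%, equivalent to 279 × 0.031/1.031 ≈ 8 completers.
- SE is 2.106 with the common slope and 2.075 with slopes by visit. Power is 91.4% and 92.1%.

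**Range.** SD of change is 14.6, σ_B 9 to 10.1, Week 1 residual SD 8 or 12, correlation AR(1) 0.85 or compound symmetry 0.6:

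| Slope, Week 1 to Week 6 | Variance excess | SE excess | Power, common slope | Power, by visit |
|---|---|---|---|---|
| −0.3 to −0.3 | 0% | 0% | 91.4–91.7% | 91.4–91.7% |
| −0.1 to −0.3 | 0.7–2.2% | 0.3–1.1% | 91.0–91.4% | 91.4–91.7% |
| −0.1 to −0.4 | 1.5–5.1% | 0.7–2.5% | 91.1–92.1% | 92.1–92.5% |
| 0 to −0.5 | 4.1–14.6% | 2.0–7.1% | 90.2–92.5% | 93.0–93.6% |

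At a gentler corner (Week 6 slope −0.25, Week 1 slope −0.10, σ_B = 7), the excess is 0.14 to 0.76% across AR(1) 0.70 to 0.95 and compound symmetry 0.6. At a steep one (Week 6 slope −0.50, Week 1 slope −0.10, σ_B = 10.1, residual SD 8 to 16), it is about 8% at AR(1) 0.90 and 11% at AR(1) 0.95. The last table row goes further because it also sets the Week 1 slope to zero.

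**Simulation.** Both unstructured MMRMs were fitted with 124 per arm and about 26% missing-at-random dropout (300 replicates per scenario, σ_B = 9, AR(1) 0.85, Week 1 residual SD 8). The ratio of model SEs, common slope to by visit, was 0.998, 1.005, 1.014 and 1.041 for the four rows in order. Mean treatment estimates from the two models differed by no more than 0.02 points. With equal slopes the SE moved from 2.001 to 2.004, which is the price of the extra term when it is not needed.

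**The case against.** A common baseline slope is a legitimate prespecified model, stated alike in protocol and SAP. Nothing in the documents says that the slope changes over time, and if it does not, the extra term gains nothing. Every magnitude above comes from assumed inputs, and the result is sensitive to them: the same slopes give half the inflation or less when the Week 1 residual SD is 12 instead of 8. The term is also not strictly free, and it does not suit every model that cites SAP 5.9.2. All of this stands, and it limits the point to an optional efficiency gain.

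A reader might go further and infer that the primary test is biased, that its type I error is wrong, or that the trial is underpowered. The documents do not support any of these. Treatment is randomised, so under-adjusting for baseline does not shift the comparison. The unstructured covariance absorbs the misfit into the Week 6 variance, so the reported SE reflects it. Power was computed without baseline adjustment and stayed at 90.2% or above under the common slope in every case in the table. One limit applies: the point about the SE relies on the unstructured matrix. A constrained fallback structure need not absorb the misfit, and SAP 5.9.2 does not carry over the sandwich estimator that protocol 9.3.2 names for that event.

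In favour of the change, the SAP's imputation step already allows what the analysis model rules out. The code in SAP 9.6.1 imputes from a joint normal model for treatment, baseline and all visits, which leaves each visit's regression on baseline free. The imputed data are then analysed with the common slope.

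**Conclusion.** The point holds as a conditional, nearly free gain in precision and is minor. SAP 5.9.2 and 5.10.2 fit one baseline slope across six visits although only Week 6 is tested. If slopes are equal, nothing is lost. Over plausible assumed values (Week 1 slope −0.10, Week 6 slope −0.25 to −0.40, baseline SD 7 to about 10), Week 6 variance is roughly 0.2 to 5% larger than it need be. That is up to about 2.5% of the SE, equivalent to about 1 to 13 of 279 completers. Values of 8 to 11% need a Week 6 slope near −0.50, wide baseline spread and strongly correlated visits; only a slope running from 0 to −0.50 goes beyond that. Validity and the stated power are unaffected.

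**What to change.** Before unblinding, add baseline-by-visit as a fixed effect to the PANSS model in SAP 5.9.2 and the CGI-S model in SAP 5.10.2. Make the same change in the MMRMs fitted to the imputed datasets (SAP 5.9.3.2, 5.10.3 and 9.6), so that the imputation and analysis models agree on baseline. The SAP already extends the protocol model by adding geographic region, so this can be recorded in the same way.

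Because other analyses cite SAP 5.9.2, state where the term does not apply. BACS and SF-6D have one post-baseline visit, so the interaction does not exist there. CGI-I has no baseline score. Allow the term to be dropped in small subgroups: SAP 5.9.4 permits groups down to 10% of the mITT set, about 37 of 372 participants over three arms, where five more parameters are not trivial.

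The cost is one model term (five parameters with six visits) and no new data. If the slopes are in fact equal, the expected SE increase is negligible.
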